### **9.6 Procedures for Reporting any Deviation(s) from the Original Statistical Plan**

Any deviation(s) from the original statistical plan will be described and justified in the final report.

### **9.7 Inclusion in Analysis**

All randomised participants, who have completed the trial and have not withdrawn their consent from their involvement in the trial, will be included in the analyses.

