#### **6.4.5 Subsequent assessments**

Second appointment – Fitting of insoles face-to-face visit at NHS GGC GRI Orthotic clinic, as per standard practice

1. Participant receives a reminder call from the PI the day before appointment to confirm attendance
2. PI fits the insoles
3. Participant is advised to wear the insoles for 10 minutes before leaving the clinic
4. If any issues arise during the 10 minutes, PI adjusts the insoles (repeat until no issues when leaving the clinic)
5. PI documents adjustments made against the unique participant number on the excel data sheet.
6. If the participant is unable to wear the insoles for any reason they will exit the trial at this stage which will be documented as “unable to proceed”. In these instances the participant will be transferred back to the standard orthotic clinic for ongoing treatment as appropriate, and an appointment will be offered within the standard waiting time of 12 weeks at the NHSGGC Orthotic Clinic unless unsuitable for the participant.
7. If continuing within the trial, the participant will be invited to attend a telephone appointment in 4 weeks with the PI
8. Participant completes the FHSQ and the PI calculates the FHSQ scores using the validated FHSQ calculation, and documents these against the unique participant number on the excel data sheet.
9. Participant is asked if there has been any change to their use of any of the following groups of medications: Biologics, DMARDs, NSAIDs, oral steroids, or analgesics. This is documented by the PI on the CRF.
10. Participant is asked to keep a daily diary documenting the total number of hours per day that the insoles were worn for.

Third Appointment – 4 Week Review

1. Participant receives a reminder call from the PI the day before appointment to confirm attendance.
2. Participant attends the telephone clinic
3. If the participant is unable to wear the insoles for any reason they will exit the trial at this stage which will be documented as “unable to proceed”, in these instances the

participant will be transferred back to standard orthotic clinic for ongoing treatment as appropriate, and an appointment will be offered within the standard waiting time of 12 weeks at the NHSGGC Orthotic Clinic unless unsuitable for the participant.

4. If continuing with the trial the participant completes the FHSQ
5. Participant reports the daily wear-time of the insoles according to their diary over the past 4 weeks.

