#### Fourth Appointment – 8 Week Review

1. Participant receives a reminder call from the PI the day before appointment to confirm attendance.
2. Participant attends the telephone clinic
3. If the participant is unable to wear the insoles for any reason they will exit the trial at this stage which will be documented as “unable to proceed”. In these instances participant will be transferred back to standard orthotic clinic for ongoing treatment as appropriate, and an appointment will be offered within the standard waiting time of 12 weeks at the NHSGGC Orthotic Clinic unless unsuitable for the participant.
4. If continuing with the trial Participant completes the FHSQ
5. Participant reports the daily wear-time of the insoles according to their diary over the past 4 weeks.
6. Participant is asked if there has been any change to their use any of the following groups of medications: Biologics, DMARDs, NSAIDs, oral steroids, or analgesics. This is documented by the PI on the CRF.
7. Participant is invited to attend a telephone appointment in 4 weeks with the PI
8. PI calculates the FHSQ scores using the validated FHSQ calculation, and documents these against the unique participant number on the excel data sheet.
9. PI records the daily wear-time, documenting these against the unique participant number on the excel data sheet.

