#### Fifth Appointment – 12 Week Review

1. Participant receives a reminder call from the PI the day before appointment to confirm attendance.
2. Participant attends the telephone clinic
3. If participant unable to wear the insoles for any reason they will exit the trial at this stage documented as unable to proceed. In these instances participant will be transferred back to standard orthotic clinic for ongoing treatment as appropriate, and an appointment will be offered within the standard waiting time of 12 weeks at the NHSGGC Orthotic Clinic unless unsuitable for the participant.
4. If continuing with the trial Participant completes the FHSQ and OPUS

5. Participant reports the daily wear-time of the insoles according to their diary over the past 4 weeks.
6. Participant is asked if there has been any change to their use any of the following groups of medications: Biologics, DMARDs, NSAIDs, oral steroids, or analgesics. This is documented by the PI on the CRF.
7. The participant is thanked for their involvement in the trial, and provided with contact details and self-referral information for the NHS GGC Orthotic Department so that they can continue to access standard care from the department in future on request.
8. PI calculates the FHSQ and OPUS scores using the validated FHSQ and OPUS calculation, and documents these against the unique participant number on the excel data sheet
9. PI records the daily wear-time, documenting these against the unique participant number on the excel data sheet.

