## **6.5 Definition of End of Trial**

The trial will conclude when either of the two conditions:

1. The recruitment phase has run for 9-months (plus 12-week follow up of all participants)
2. Participant recruitment = 114 (plus final 12-week follow up of all participants)

AND

- All the enrolled participants have concluded all 5 appointments, and all the data has been entered into the excel data sheet.

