## **6.6 Discontinuation/ Withdrawal of Participants from Study Treatment**

During the course of the trial a participant may choose to withdraw early from the trial at any time. This may happen for a number of reasons, including but not limited to:

- The occurrence of what the participant perceives as an intolerable AE.
- Inability to comply with trial procedures
- Participant decision

The following options for withdrawal from the trial are included on the PIS:

1. Participants can withdraw from the study but permit data obtained up until the point of withdrawal to be retained for use in the study analysis. No further data would be collected after withdrawal.
2. Participants can withdraw completely from the study and withdraw the data collected up until the point of withdrawal. The data already collected would not be used in the final study analysis.

In addition, the PI may discontinue a participant from the trial treatment at any time if the Investigator considers it necessary for any reason including, but not limited to:

- Ineligibility arising during the trial – i.e. development of a medical condition as outlined in the exclusion criteria.

- Significant non-compliance with treatment regimen or trial requirements – i.e. participant has not worn or unable to wear the insoles between appointments
- An adverse event which requires discontinuation of the CAD/CAM insoles or results in inability to continue to comply with trial procedures
- Disease progression which requires discontinuation of the CAD/CAM insoles – i.e. medically too unwell to continue participation, or disease progression as outlined in the exclusion criteria

The type of withdrawal and reason for withdrawal will be recorded in the CRF.

If the participant is withdrawn due to an adverse event, the Investigator will arrange for follow-up visits or telephone calls until the adverse event has resolved or stabilised.

All participants withdrawn from the trial for any reason, will be offered an appointment at the general NHS GGC Orthotic service to resume their standard care. Contact information for the NHS GGC Orthotic Department is included within the PIS.

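### Section 9.7 restricts the analyses to trial completers, so on a plain reading participants who cannot wear their insoles drop out of the between-arm pain comparison, and Sections 9.1, 9.5 and 6.6 do not settle whether they return

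*Combined protocol and SAP*

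**What the plan says.** Section 9.7 includes in the analyses "All randomised participants, who have completed the trial and have not withdrawn their consent from their involvement in the trial". It does not define completion and names no other set. The nearest guide is the end-of-trial condition in Section 6.5: "All the enrolled participants have concluded all 5 appointments".

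Exit rules are in Section 6.4.5:

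- Second appointment (fitting), step 6: "If the participant is unable to wear the insoles for any reason they will exit the trial at this stage". The first FHSQ comes later, at step 8: "Participant completes the FHSQ and the PI calculates the FHSQ scores using the validated FHSQ calculation".
- 4-week and 8-week reviews: the same exit rule at step 3, with the questionnaire at step 4 conditional on staying in. The 8-week text is "If continuing with the trial Participant completes the FHSQ".
- 12-week review, step 3: "If participant unable to wear the insoles for any reason they will exit the trial at this stage documented as unable to proceed". The final FHSQ and OPUS follow at step 4.

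Section 6.6 also lets the PI discontinue trial treatment where the "participant has not worn or unable to wear the insoles between appointments". For participants who choose to withdraw, its first option is to "permit data obtained up until the point of withdrawal to be retained for use in the study analysis".

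Randomisation is at the first appointment (6.4.3, 6.4.4), before any insole is fitted. Section 9.1 names a mixed ANOVA or, for non-normal data, Friedman and Wilcoxon tests within groups and Mann-Whitney tests between groups. Section 9.5 brings in multiple imputation once missing data pass 5%. The Synopsis and Section 6.1 call the design an equivalence trial, while the null hypothesis in 9.0.2 is one of no difference.

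**The concern.** Being unable to wear the insole happens after randomisation and may be a consequence of the arm. Section 4 gives the trial's own rationale: services doubt that a scan and a cast yield matching models, and differences in volume have been reported. If one method produces more unwearable insoles, a completer analysis compares only those for whom each method worked.

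The declared design makes this matter more. In an equivalence trial, removing device failures can pull the arms together and so favour the conclusion the trial seeks. Under the no-difference null of 9.0.2, the same exclusion can hide a real difference.

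**Working it through.** **1. Who is excluded, reading the sections together**

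| Point of exit | FHSQ scores held if the listed steps are followed | Position under 9.7 |
|---|---|---|
| Fitting | possibly none (exit at step 6, FHSQ at step 8) | not a completer |
| Week 4 | baseline | not a completer |
| Week 8 | baseline, week 4 | not a completer |
| Week 12 | baseline, weeks 4 and 8 | recorded as an exit, but attended the fifth appointment; unclear under 6.5 |

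**2. Whether another section brings them back**

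- 9.1: a Mann-Whitney test at one visit could use partial data. A mixed ANOVA in its usual form drops anyone with a missed visit. The section does not say which records enter.
- 9.5: it names no population, variables or unit for the 5%. Six exits are the planned loss (57 − 54 = 3 per arm). Counted by participant, 6/114 = 5.3% and imputation applies, whereas 5/114 = 4.4% and it does not. Counted by FHSQ score, 114 × 4 = 456 are planned. Six exits at week 12 lose 6/456 = 1.3%; six at fitting with no score lose 24/456 = 5.3%. Even when imputation applies, nothing says it extends to people whom 9.7 leaves out.
- 6.6: the first withdrawal option conflicts with 9.7. It covers withdrawal chosen by the participant, and 6.4.5 does not say what happens to the data of those recorded as unable to proceed.

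**3. The plan's own sample size**

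Section 9.2 gives a difference of 13, SD 26.9, 54 per group, 5% drop-out, 57 per group and 114 in total. It states no alpha, power or sidedness, so these are assumed. A t-test calculation gives 53.6, rounded to 54, at one-sided 5% with 80% power, and 53.8, rounded to 54, at two-sided 5% with 70% power. Then 54/0.95 = 56.8, rounded to 57, and 2 × 57 = 114. The figures reproduce under either setting. The change proposed here does not alter them.

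**4. Size of the distortion (illustration)**

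Let p be an arm's exit proportion and g the gap between its completers' and exiters' mean pain change. An arm's all-randomised mean is its completer mean minus p × g. The difference that a completer analysis misses is therefore p_A × g_A − p_B × g_B. With a common gap this is (p_A − p_B) × g. Both p and g are assumptions.

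Standard error of the between-arm difference: 26.9 × √(2/54) = 5.18.

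| Exits | Assumed gap | Hidden difference | In SE |
|---|---|---|---|
| 5% v 0% | 12.5 (the minimal important difference in Section 5) | 0.05 × 12.5 = 0.63 | 0.12 |
| 5% v 0% | 20 | 0.05 × 20 = 1.0 | 0.19 |
| 5% v 0% | 30 | 0.05 × 30 = 1.5 | 0.29 |
| 10% v 0% | 20 to 30 | 2.0 to 3.0 | 0.39 to 0.58 |
| equal, same gap | any | 0 | 0 |

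The 5% v 0% rows mean about three exits in one arm and none in the other. The 10% v 0% row needs all six planned losses in one arm (6/57 = 10.5%). Section 9 states no equivalence margin, so 12.5 points is the only yardstick: 1.5/12.5 = 12%.

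**5. How much a better analysis recovers**

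Assume equal correlation r between visits, no baseline gap, and the gap present from week 4. A likelihood-based model then recovers r/(1+r) of the hidden difference for week-8 exiters and 2r/(1+2r) for week-12 exiters. At r = 0.5 these are 33% and 50%; at r = 0.3, 23% and 37.5%; at r = 0.7, 41% and 58%. For exits at fitting or week 4, recovery is nil, because no post-fitting score exists.

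**The case against.** The best case for the plan is that losses will be few and visible. Insoles are adjusted at fitting until the participant leaves without problems (6.4.5, second appointment, step 4). Drop-out rate is already a tertiary outcome. Withdrawal reasons go in the CRF (6.6), and the Co-I's list holds the randomisation code (Section 13), so exits could be tabulated by arm afterwards. All of this stands, and it limits the size. It does not supply the exiters' scores, and the drop-out outcome is not specified by arm.

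Four stronger readings are tempting, and the documents do not support them:

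- A reader might infer that the non-parametric route in 9.1 excludes exiters because Friedman tests need every visit. In 9.1 those tests serve the within-group analysis; the between-arm test is Mann-Whitney. The exclusion comes from 9.7.
- A reader might infer that exiters' earlier scores will certainly be discarded. Section 6.6 keeps some withdrawers' data for analysis, so the documents conflict.
- A reader might infer that PI discontinuation always removes someone from the trial, or that it invites selective removal. The clause concerns trial treatment, and the PI is blinded (6.4.4).
- A reader might infer a material bias towards equivalence. No exit rate or gap is given, and a 30-point gap exceeds the planning SD of 26.9.

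It can also be argued that an all-randomised set containing non-wearers may itself pull the arms together. That is fair in an equivalence setting, and is a reason to report both analyses.

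**Conclusion.** The point holds as a defect in the definition of the analysis set and should be fixed. Followed as written, 9.7 conditions the pain comparison on a device-related event after randomisation, and no other section clearly reverses that. Confidence is high on the text and low on any particular size. At the planned drop-out the effect is modest even in the one-sided 5% v 0% illustration, and would grow only if losses exceeded plan and were unequal. If exiters fared better than completers, or the worse-scoring exits fell in the other arm, the direction would change. The case for change rests on the exclusion being avoidable at little cost, and on its plausible direction being the one an equivalence trial can least afford.

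**What to change.** 1. Replace 9.7 with a set of all randomised participants, analysed as allocated, using every FHSQ score that the participant has not withdrawn, and expressly including those recorded as unable to proceed. Reconcile 6.4.5, 6.5, 6.6 and 9.7, including what counts as completion.
2. State in 9.1 and 9.5 that the pain comparison uses this set through a method that keeps incomplete records: either a likelihood-based repeated-measures model, or multiple imputation by arm that does not depend on the 5% trigger.
3. Add a missing-not-at-random sensitivity analysis that shifts exiters' imputed pain scores separately in each arm over a range fixed in advance. It is needed because items 1 and 2 recover only part of the bias, and none for exits at fitting or week 4. For scale, a 30-point shift for 3 of 57 participants moves an arm mean by 30 × 3/57 = 1.6 points.
4. Report the completer analysis alongside, given the equivalence aim, and report the existing drop-out outcome and the unable-to-proceed exits by arm and visit.

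The cost is revised text and a little more analysis; sample size and exit care are unchanged.

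Optional, and not needed for this point: record the first FHSQ before the fitting-stage exit step, so that those exiters have a baseline. Collecting the FHSQ after exit is a separate conduct choice. It would have to be reconciled with the exit wording in 6.4.5 and with the bar in 6.6 on collecting data after withdrawal, and later scores could reflect other care. Either change may need approval under 12.3 if the amendment is substantial.

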## **10. DIRECT ACCESS TO SOURCE DATA/DOCUMENTS**

Direct access will be granted to authorised representatives from the sponsor, host institution and the regulatory authorities to permit trial-related monitoring, audits and inspections.

## **11. QUALITY CONTROL AND QUALITY ASSURANCE PROCEDURES**

### **11.1 Quality control and assurance**

The study will be conducted in accordance with the current approved protocol, and standard operating procedures within the NHS GGC Orthotic Department.

Regular monitoring will be performed according to ICH GCP. Data will be evaluated for compliance with the protocol and accuracy in relation to source documents. Following written standard operating procedures, the monitors will verify that the clinical trial is conducted and data are generated, documented and reported in compliance with the protocol, GCP and the applicable regulatory requirements.

### **11.2 Peer review**

This protocol has been peer reviewed by the supervisory team at the University of Central Lancashire.

## **12. ETHICS**

### **12.1 Declaration of Helsinki**

The Investigator will ensure that this study is conducted in accordance with the principles of the Declaration of Helsinki.

### **12.2 ICH Guidelines for Good Clinical Practice**

The Investigator will ensure that this study is conducted in full conformity with relevant regulations, with the ICH Guidelines for Good Clinical Practice (CPMP/ICH/135/95) July 1996, and the UK policy Framework for Health and Social Care research.

### **12.3 Approvals**

The protocol, informed consent form, participant information sheet and any proposed advertising material will be submitted to an appropriate Research Ethics Committee (REC) for written approval. No participants will be entered into the study until approvals have been received.

The Investigator will submit and, where necessary, obtain approval from the above parties for all substantial amendments to the original approved documents.

### **12.4 Participant Confidentiality**

The trial staff will ensure that the participants' anonymity is maintained. The participants will be identified only by a unique participant number on the CRF and the excel data sheet. All electronic documents will be stored securely within a registered GDPR asset folder, and only accessible by trial staff and authorised personnel. The study will comply with the Data Protection Act 1998 which requires data to be anonymised as soon as it is practical to do so.

### **13. DATA HANDLING AND RECORD KEEPING**

All study data will be entered on a Microsoft excel spreadsheet, saved within a GDPR registered asset folder as per standard operating procedure in the NHS GGC Orthotics Department. Regular backups of the electronic data will be performed by the PI. The participants will be identified by a unique participant number only. The name and any other identifying detail will NOT be included in any study data electronic file. The Co-I will keep a list containing all subjects enrolled into the study. This list remains with the Co-I and is used for unambiguous identification of each subject. The list contains the unique participant number, full name, date informed consent signed, date of screening, the unique hospital number (CHI), and the randomisation group code. A copy of the participant's consent and enrolment in the study will be recorded in the participant's medical record. This data will identify the study and document the dates of the participant's participation.

#### **Archiving:**

Although not required by law for non-CTIMPs, in line with the principles of ICH GCP essential study documents will be retained for up to a minimum of 5 years following the completion of the study. Arrangements for confidential destruction will then be made. If a participant withdraws consent for their data to be retained, it will be confidentially destroyed immediately. No records/study documentation/data may be destroyed without first obtaining written permission from the Sponsor.

Essential documents could include (this list is not exhaustive):

Signed informed consent documents for all participants.

Participant identification code list, screening log and enrolment log.

Record of all communications between the Investigator, the REC and the Sponsor.

Composition of the REC, and the Sponsor

List of sub-investigators and other appropriately qualified persons to whom the Investigator has delegated significant study-related duties, together with their roles in the study and their signatures.

Copies of case report forms and documentation of corrections for all participants.

All other source documents (subject medical records, hospital records, etc.).

All other documents as listed in section 8 of the ICH E6 Guideline for Good Clinical Practice (Essential Documents for the Conduct of a Clinical Trial).

Normally, these records will be held in the Investigator's archives. If the Investigator is unable to meet this obligation, he or she must ask the Sponsor for permission to make alternative arrangements. Details of these arrangements should be documented.

#### **14. FINANCING AND INSURANCE**

The time and cost associated with the study has been agreed in kind by the NHS GGC Orthotic Service.

The PI has been funded for a 12-month Careers Fellowship by NHS Education Scotland, to support the PI's research activities associated with this trial.

NHS bodies are legally liable for the negligent acts and omissions of their employees. If you are harmed whilst taking part in a clinical trial as a result of negligence on the part of a member of the study team this liability cover would apply.

Non-negligent harm is not covered by the NHS indemnity scheme. The NHS Greater Glasgow and Clyde Health Board, therefore, cannot agree in advance to pay compensation in these circumstances. In exceptional circumstances an ex-gratia payment may be offered.

